A Transition of Care Model from Hospital to Community for Hispanic/Latino Adult Patients with Diabetes

Document Date: November 9, 2021

NCT04864639

Purpose of the Study

The prevalence of diabetes in adults over the age of 20 is significantly higher in the Hispanic/Latino population compared to non-Hispanic whites. Admitted patients with diabetes are at higher risk for readmission and Emergency Department (ED) visits than those without diabetes especially those in lower socioeconomic status and racial/ethnic minority groups. The goals of this proposed study are to explore patients and providers perceptions (n=15, 6 providers and 4 patients) of the current discharge process which will inform the development of a patient-centered transition of care model for Hispanic /Latino adults (≥ 18 years of age) with diabetes from hospital to the community. It is hypothesized that a culturally tailored transition of care model tailored for Hispanic/Latinos adults with diabetes will result in fewer ED visits, hospital admissions, and re-admissions.

The objective remains the same for Aim2. Our hypothesis is that participants enrolled in the newly developed transition of care model will have less Emergency Room visits post discharge, lower rates of unplanned readmission at 30 days post discharge and will report more follow up visits with a health care provider within 30 days of discharge than those individuals discharged on the usual transition of care plan. In addition, patient experience will be better in those in the new transition of care model.

Background & Significance

The prevalence of diabetes in adults over the age of 20 is significantly higher in the Hispanic/Latino population compared to non- Hispanic whites. Diabetes imposes a large economic burden partially due to the significantly higher rates of hospital admission compared to those individuals without diabetes. In 2014, a total of 7.2 million hospital discharges were reported with diabetes as any listed diagnosis among U.S. adults aged 18 years or older. Admitted patients with diabetes are at higher risk for readmission and Emergency Department (ED) visits than those without diabetes especially those in lower socioeconomic status, racial/ethnic minority groups, history of prior admission, diabetes associated comorbidities, public insurance, and emergent or urgent admission.

Diabetes is one of the most common conditions managed in the hospital, yet how to transition a patient with diabetes to the outpatient setting is understudied and outcomes of patients with diabetes after discharge is unknown. The importance of the transition of care from hospital to the community for patients with diabetes has been identified as a major area of improvement in diabetes care. Despite the economic burden and growing interest in factors leading to readmission, a paucity of research exists focusing on the transition of care among patients with diabetes. The American Diabetes Association (ADA) recommends a well-structured, patient-centered, transitions of the care, which includes a discharge plan and follow up within 30 days from discharge to help reduce the rates of readmission as well as a hospital stay. Unfortunately, this transition is significantly challenging for patients with fewer resources, language barriers, cultural differences, and low health literacy which collectively can lead to an increase risk of readmissions and emergency department visits. Further, the limited available data looking at outcomes post-discharge in patients with diabetes shows that being Hispanic/Latino is associated with a higher risk for multiple hospitalizations and re-hospitalization. Despite the increasing

advances in diabetes care, Hispanic/Latino patients remain a leading subgroup of patients not reaching diabetes goals. Therefore, developing a transition of care model that is patient/culturally centered for Hispanic/Latino adults with diabetes from the hospital to the community/home will reduce the existent gap in diabetes care.

Design & Procedures

Aim 1: To develop the transition of care model for Hispanic/Latino adults, patients and providers will be selected from Duke Regional Hospital (DRH) and Duke University Health System (DUHS), the local Hispanic/Latino community, and local clinics in Durham delivering care to Hispanic/Latino patients with diabetes. Drs. [name] and [name] will collect the data. It is anticipated that a total of 15 participants (4 patients) and (6 providers - physicians [MD, DO], nurse practitioners (NPs), and physician assistants (PAs)) will be obtained. We seek to explore patients' and providers' perspectives on the transition of care from hospital to community. All participants will complete a brief questionnaire. The information collected will be instrumental in developing a transition of care model that is culturally/patient centered.

Aim 2: Overall common themes have been collected from the 4 patient participants and 6 provider participants interviews and questionnaires thus far. Providers and patients uniformly expressed a need for a simple discharge summary that is more visual and in Spanish, language barriers and financial constraints.

Duke CTSI will conduct a Community Consultation Studio with community Engaged Research Initiative Core as a part of Pro00103450. They will interview 6-8 participants from Hispanic/Latino communities with diabetes. The common themes from this interview along with the common themes from the first 10 participants in this protocol will be combined to develop a transition of care model.

The first set of 16 participants will be discharged on the newly developed model based on interviews and data collected already and CTSI CCS protocol Pro00103450. The participants will be asked to complete a set of questionnaires and a 30-day post discharge telephone interview.

This interactive approach will use the Plan-Do-Study-Act (PDSA) framework. Changes can be reassessed and modified swiftly as a part of the continuous improvement cycle to allow for adjustments that facilitate the desired outcomes.

The second set of 16 participants will be discharged on a model based on the first 16 participants experience and feedback. Five participants enrolled in the first set will be re-interviewed to assess their feedback regarding the process. Based on this information the TOC model will be revised.

The second set of participants will complete a set of questionnaires and a 30-day post discharge phone interview similar to the first set of participants.

Key personnel will administer informed consent, eConsent or verbal consent depending on the participants access to resources at the time of enrollment. Covid-19 face to face interactions has limited the ability of face to face contact strictly for research purposes. We would like to keep the face to face option available for consent and questionnaires because some participants may be recruited by the key personnel rounding on the patient.

The Hispanic/Latino population has limited access to e-mail and smart phones. In the event that participants do not have access to email and cellphone we will obtain verbal consent. The informed consent, questionnaires and 30 day follow up phone call may all be done verbally in these cases. The 30 day follow telephone call will be recorded with an encrypted recorder. The recording will be used for review purposes only.

The 30-day follow up telephone survey will also collect data from participants receiving care outside of the Duke University Health System and systems not sharing the same electronic medical record.

3 additional providers will be reconsented and repeat the original interview.

Selection of Subjects

Aim 1 inclusion criteria:

Patients:

1. 18 years or older
2. Self-Identified as Hispanic/Latino
3. Previous diagnosis with Diabetes Mellitus
4. Ability to provide informed consent without a proxy
5. An admitted patient at a Duke University Hospital or Duke Regional Hospital facility.
6. English or Spanish speaking

Providers:

1. See patients at Duke Regional Hospital or Duke University Hospital
2. Working in the local clinics proving care for the local Hispanic/Latino patients.

For Aim 2 the patient inclusion criteria will only include patients that are currently hospitalized. There is not exclusion criteria based on comorbidities.

Subject Recruitment and Compensation

Subjects will be introduced to the study by [name], [name] or other key personnel. They are both bilingual. Approximately 4 patients will be recruited from Durham, NC. Inclusion criteria include age ≥ 18 years, self-identified as Hispanic/Latino, previous diagnosis of diabetes, Spanish and/or English speaker, ability to provide informed consent without a proxy, with a recent (within 3 months) hospitalization at Duke Regional Hospital (DRH) or Duke University Hospital. Maestro care/Epic slicer dicer will be used to

identify participants with a recent hospitalization. Patient word of mouth may also be used from local Hispanic organizations. Both methods have been previously implemented by Co-PI ([name]) while enrolling Hispanic/Latino participants in research studies. Approximately 6 health care providers will be recruited from the DRH and Duke University Hospital. We aim to enroll a diverse group of providers including MDs, DOs, NPs and PAs. Providers will be approached for recruitment by the Co-PIs or designated trained research staff. Both inpatient and outpatient providers will be targeted. Compensation will be \$10 per person. If the participant is not interested in sharing their social security number with the research team they will receive a gift of similar monetary value.

Aim 2: Participants will be recruited using Slicer Dicer or the inpatient diabetes admission list. Trained key personnel on the study will introduce the potential subjects to the study. A total of 32 subjects will be recruited and enrolled. The subjects will be compensated \$25 dollars from petty cash for their participation. For the re-interviews (providers) will receive \$10 dollars.

Risk/Benefit Assessment

This is a minimal risk study. We will not include vulnerable populations.

This study should result in better understanding of factors that impact the transition of care of Hispanics/Latinos patients with diabetes. Identifying and understanding internal and external barriers to the transition of care should be determined when considering designing a culturally sensitive transition of care model. A better method to transition from inpatient setting to home for Hispanic/Latinos with regard to factors such as lower socioeconomic status, language, and health literacy along with a fragmented delivery system may result in better outcomes during the transition phase from acute to the outpatient setting.

The benefits to the subject are that the participant may require fewer visits to the ED and less admissions to the hospital in the 30 days following their hospitalization.

The importance of this study is to optimize the transition of care of Hispanic/Latino patients with diabetes because it is poorly understood. This study will inform a more aligned discharge and follow-up process for Hispanic/Latino patients discharge in future and will also inform future larger randomized trials.

Data Analysis & Statistical Considerations

General Data Analytics. The recording will be reviewed by the Co-PI, each independently, they will identify themes and will color code them. Subsequently themes will be combined into common themes.

Analysis. For all outcomes and demographic information collected, descriptive analysis (means and standard deviations for continuous variables and frequencies and percentages for categorical variables) overall and by randomization arms. The non-feasibility outcomes will be compared

between the usual care and intervention group. Chi-squared or Fisher's Exact tests will be conducted to assess the differences of each outcome between groups. Logistic regression models will be conducted to access the adjusted differences of each outcome between usual care and intervention groups. The models will be adjusted for a limited number of variables that are theoretically thought to explain some variation in the value of the outcomes.

For Aim 2 we would like to ensure that we are able to at minimum detect a difference in the primary outcomes in the number of Emergency Department visits and hospital re-admissions.

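### The Aim 1 total is given as 15, but the patients and providers listed beside it add up to 10

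*Combined protocol and SAP*

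**What the plan says.** Purpose of the Study gives the size of the exploratory interview stage as "n=15, 6 providers and 4 patients". The Aim 1 paragraph of Design & Procedures repeats it: "It is anticipated that a total of 15 participants (4 patients) and (6 providers", followed by the eligible professions. That paragraph draws participants from the two Duke institutions, "the local Hispanic/Latino community, and local clinics in Durham delivering care to Hispanic/Latino patients with diabetes", with no number for any source.

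The Aim 2 text in the same section reports what has been done: "Overall common themes have been collected from the 4 patient participants and 6 provider participants interviews and questionnaires thus far". It then says that "the common themes from the first 10 participants in this protocol will be combined" with themes from a community studio run under a separate protocol.

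Subject Recruitment and Compensation sets approximate targets of 4 patients and 6 providers. The provider target names only the two hospitals, although Selection of Subjects also lists work in local clinics among the provider criteria.

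Three other groups have a number attached:
- The studio: "They will interview 6-8 participants from Hispanic/Latino communities with diabetes".
- The Aim 2 feedback step: "Five participants enrolled in the first set will be re-interviewed".
- A line just before Selection of Subjects, under which three providers will give consent again and go through the initial interview again. That line calls them additional and states no aim.

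**The concern.** A stated sample size should equal the sum of the parts listed with it. Here the total and the parts disagree inside one sentence, and the same disagreement appears in two separate sections, so a single slip of the pen or a text-reading fault is an unlikely explanation.

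What is at stake is the reported size of Aim 1. From the total, Aim 1 looks five people short; from the split, it looks complete. If five more people are intended, the protocol does not say whether they are patients or providers, or where they would come from.

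**Working it through.** **Inputs**
- Stated Aim 1 total: 15 (Purpose of the Study; Design & Procedures, Aim 1).
- Parts given with it: 4 patients and 6 providers (same two places).
- Interviews completed: 4 patients and 6 providers, also counted as the first 10 (Design & Procedures, Aim 2).
- Recruitment targets: about 4 patients and about 6 providers (Subject Recruitment and Compensation).
- Other groups with a number: 3 providers consented again, 6 to 8 studio participants, 5 Aim 2 re-interviews (Design & Procedures).

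**Step 1: reproduce the stated total.** Total = patients + providers = 4 + 6 = 10. The stated 15 is not reproduced. The gap is 15 − 10 = 5, which is 5/10 = 50% above the sum of the parts.

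**Step 2: compare the other Aim 1 counts.** Completed interviews: 4 + 6 = 10. Recruitment targets: about 4 + about 6 = about 10. The 4/6 split is the same wherever it is given; only the total conflicts.

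**Step 3: see whether another group closes the gap.**

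| Added to the 10 | Result | Can it explain 15? |
|---|---|---|
| 3 providers, if all are new people | 10 + 3 = 13 | No, still 2 short |
| Studio participants | 10 + 6 = 16 to 10 + 8 = 18 | No; also under a separate protocol |
| 3 providers and studio | 13 + 6 = 19 to 13 + 8 = 21 | No |
| 5 Aim 2 re-interviews | 10 + 5 = 15 | In number only |

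The last row matches in number but not in substance. Those five come from the first set of 16 discharged on the new model, so they are already within the Aim 2 total of 16 + 16 = 32, and they are asked about the new process. The 15 in Purpose of the Study concerns views of the existing discharge process.

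**Step 4: sources without numbers.** The local community and local clinics say where participants may come from. They add no one beyond the 4 and 6, because the 15 is itself broken down as 4 and 6.

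**The case against.** The strongest counter-reading is that 15 is a ceiling and 10 is enrolment to date. The Aim 2 text describes themes gathered so far and speaks of the first ten participants, which leaves room for more. Those two statements also report completed interviews with the same ten people, so they are one piece of evidence rather than two and do not independently confirm a planned total of 10. The separate planned figures, the recruitment targets, are only approximate.

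All of that stands, and it bears on which figure is wrong. It does not remove the contradiction. The protocol nowhere calls 15 a ceiling, the forward-looking Aim 1 sentence itself breaks the 15 into 4 and 6, and the recruitment targets follow the same split. The reference to the first ten may simply distinguish them from the later Aim 2 sets.

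The three providers are a fair second objection. Their description as additional points to new people; consenting again and repeating the interview point to people already counted. The compensation paragraph pays providers for re-interviews, which favours repeats but does not settle it. So the documents do not support a rule that these three always fall outside the total. Even counted as new, they reach only 13.

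A reader might also infer that any further five would play no part in building the model. That goes too far. The Aim 1 paragraph gives the information from its participants a role in developing the model. Only the later Aim 2 text narrows the inputs to the initial version, which rests on the first ten, the studio and what was in hand ("based on interviews and data collected already and CTSI CCS protocol Pro00103450").

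**Conclusion.** Wrong as written, minor. The Aim 1 total of 15 exceeds the sum of its stated components by five people, in two places, and no other group with a number accounts for the difference. The arithmetic needs no assumptions. That 10 is the likelier intended figure is a judgement, based on the consistent 4/6 split and the matching targets; the documents do not say which number is in error.

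Two stronger conclusions are tempting and unsupported. One is that Aim 1 has under-recruited by five: the 4 and 6 named in the plan have been interviewed, and nothing shows that five more were ever defined. The other is that the trial's comparison is affected: the figure enters no test or power calculation, and Aim 2 has its own total of 32. The consequence is limited to the Aim 1 sample size as reported.

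**What to change.** In Purpose of the Study and in the Aim 1 paragraph of Design & Procedures, restate the total as 10 (4 patients + 6 providers). If 15 is an intended ceiling, keep it, give the patient/provider split of the remaining five, and change the targets in Subject Recruitment and Compensation to match.

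In either case, state whether the three providers consented again are new or are among the six. If they are repeats, the headcount is unaffected. If they are new Aim 1 participants, the base becomes 4 + 9 = 13, and a ceiling of 15 would leave 15 − 13 = 2 to define.

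**Cost.** Correcting to 10 changes two figures and adds one clarifying sentence on the three providers. If the three are new, the provider count changes as well. Keeping 15 also means revising the split and the targets and recruiting the people still outstanding. Neither route changes the Aim 2 size or analysis.

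### Does the Aim 2 analysis go wrong because it plans no results by set, although the second set of 16 gets a revised model?

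*Combined protocol and SAP*

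**What the plan says.** Under Design & Procedures, Aim 2, the first 16 participants leave hospital on the model built from the interviews and the community consultation. Five of them are re-interviewed, and "Based on this information the TOC model will be revised". The next step is: "The second set of 16 participants will be discharged on a model based on the first 16 participants experience and feedback". The work follows a Plan-Do-Study-Act (PDSA) cycle, of which the protocol says: "Changes can be reassessed and modified swiftly as a part of the continuous improvement cycle". Data collection is alike in the two sets: the second set completes questionnaires and "a 30-day post discharge phone interview similar to the first set of participants".

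Subject Recruitment and Compensation gives the size: "A total of 32 subjects will be recruited and enrolled". The Aim 2 hypothesis in Purpose of the Study speaks of "participants enrolled in the newly developed transition of care model" and sets them against patients on the usual plan. Data Analysis & Statistical Considerations calls for descriptive summaries "overall and by randomization arms", then tests and logistic models of usual care against intervention. It mentions neither set nor model version. Risk/Benefit Assessment adds that the study "will also inform future larger randomized trials".

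**The concern.** The design changes the intervention halfway through on purpose, and the analysis text does not mention the change. Read literally, the listed analyses give no separate figure for the revised model, yet a revised version is what the team will hold when the study ends and might take into a larger trial. If the two versions performed differently, a combined rate would describe neither. A reader given only 6 events in 32 could not tell 3 and 3 from 5 and 1.

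The PDSA wording adds a second worry. If the model can be changed quickly, set number may not identify the version a patient received, and the protocol describes no log of versions. At stake would be how well the pilot's outcome figures describe the model carried forward.

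**Working it through.** **Reproducing the plan's figure.** 16 + 16 = 32, which matches the stated total. The plan gives no event rate, effect size, significance level or dropout figure, so every count below is an assumption chosen for illustration.

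**What the plan sets out to estimate.** The hypothesis names one transition model and one comparator, usual care. The analysis section has the same single contrast. No objective asks for an effect by version or for a comparison of the first set with the second. Under a PDSA design, the thing evaluated can properly be the evolving programme, and the figure for all 32 describes it. The revision itself is judged mainly through participants' experience and feedback, the five re-interviews and the coding of themes from recordings. Those steps are planned.

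**Can results by set still be obtained?** Yes. The sets are sequential, so enrolment order should identify them, and both complete similar questionnaires and a 30-day call. Nothing is lost by not naming the table in advance.

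**How far can the combined rate lie from the second set's rate?** With n1 and n2 analysed,

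gap = combined rate − set 2 rate = n1/(n1 + n2) × (rate 1 − rate 2).

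| Set 1 | Set 2 | Combined | Gap (percentage points) |
|---|---|---|---|
| 3/16 | 3/16 | 6/32 = 18.75% | 0.5 × (18.75 − 18.75) = 0 |
| 4/16 | 2/16 | 6/32 = 18.75% | 0.5 × (25 − 12.5) = 6.25 |
| 5/16 | 1/16 | 6/32 = 18.75% | 0.5 × (31.25 − 6.25) = 12.5 |
| 4/16 | 2/12 | 6/28 = 21.4% | 16/28 × (25 − 16.67) = 4.8 |
| 4/12 | 2/16 | 6/28 = 21.4% | 12/28 × (33.33 − 12.5) = 8.9 |

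This arithmetic holds for any study in two sets. It shows what could happen, not what is expected here.

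**Could figures by set reveal such a gap?** Exact (Clopper-Pearson) 95% intervals:

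- 2/16: 1.6% to 38.3%
- 4/16: 7.3% to 52.4%
- 6/32: 7.2% to 36.4%

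The interval for 2/16 is 38.3 − 1.6 = 36.7 points wide and contains the whole interval for 6/32. A gap of 6.25 points is invisible at that precision. Fisher's exact two-sided p is 0.65 for 4/16 against 2/16 and 0.17 for 5/16 against 1/16.

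Exact Fisher power with 16 per set, at an assumed two-sided 0.05:

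| Assumed rates | Power |
|---|---|
| 25% v 12.5% | 6.8% |
| 30% v 10% | 16.8% |
| 50% v 25% | 18.4% |

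A split by version within a set would be weaker still: 1/8 has an interval of 0.3% to 52.7%.

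**Is version really detached from set?** The sentence on swift changes is a general description of PDSA. The text that follows it lays out one revision, placed between the sets and fed by the first set's experience. Changes within a set are possible but nowhere planned.

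**The case for a change.** The best case for the concern does not rest on significance tests. It runs as follows. A table by set costs almost nothing. Low precision is a reason to show intervals, not to leave figures out. Naming the table in advance would guard against reporting only the more favourable set. And while set can be rebuilt from enrolment order, the version used at a given discharge may not be recoverable later if the model does change within a set.

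Much of this stands as advice. A by-set table labelled as descriptive, non-randomised and confounded with calendar time would be sensible reporting, and noting the version at discharge would be a harmless precaution. But none of it shows a fault. The point about versions needs two things the protocol does not say: that changes will occur within a set, and that no record of them will be kept. The second is inferred from silence in a very short document. Selective reporting is a general risk, and nothing in this plan points to it; the summaries it does name include the overall figure.

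**Conclusion.** The concern does not hold. The textual observation is accurate: two sets, an initial and a revised model, and no by-set output in the analysis section. But the combined figure over 32 is a legitimate answer to a hypothesis worded for one model, the data for each set are collected in any case, and figures from 16 patients could not show whether the revision helped. In the illustrations the combined rate differs from the second set's rate by 0 to 12.5 points, against an interval about 37 points wide for 2/16. No stated number, rule or conclusion would change if the table were added. What remains is a reporting preference.

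This rests on assumed event counts, on sets identifiable from enrolment order, and on the model being revised between sets as the protocol describes. It says nothing about a different question: the analysis section refers to randomization arms and a usual-care group, while the Aim 2 design places both sets on a new model and describes no randomisation. A table by set would not resolve that.

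### No between-group method is named for an ordinal or continuous patient-experience score, and the measure itself is not defined

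*Combined protocol and SAP*

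**What the plan says.** All references are to the combined protocol and SAP.

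- **Purpose of the Study** states the Aim 2 hypotheses on emergency visits, readmissions and follow-up visits, then adds: "In addition, patient experience will be better in those in the new transition of care model".
- **Design & Procedures, Aim 2** describes data collection: "The participants will be asked to complete a set of questionnaires and a 30-day post discharge telephone interview". It does not say which of these records patient experience, and it names no instrument, scale, score or cut-point.
- **Data Analysis & Statistical Considerations** opens the comparison with "The non-feasibility outcomes will be compared", between usual care and intervention. The unadjusted method is "Chi-squared or Fisher's Exact tests will be conducted to assess the differences of each outcome between groups". The adjusted method is "Logistic regression models will be conducted to access the adjusted differences of each outcome between usual care and intervention groups". Continuous variables appear only in the descriptive sentence: "means and standard deviations for continuous variables and frequencies and percentages for categorical variables". No rank test, trend test, t-test or linear model is named.
- The same section names emergency department visits and hospital readmissions as the primary outcomes.
- **Subject Recruitment and Compensation** gives the size of Aim 2: "A total of 32 subjects will be recruited and enrolled".

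**The concern.** A claim that experience will be better is directional and is naturally tested on an ordered scale. The stated unadjusted test leaves two ways to handle such a scale.

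The first is to treat the levels as unordered categories. That test gives the same p-value if the levels are relabelled in any order, so it asks whether the distributions differ, not whether one is better. The second is to collapse the scale to two levels. That keeps a direction but discards information, and it needs a cut-point that could be picked after seeing the data.

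Either way, a real improvement is more likely to be reported as no difference. The test also gives no estimate of how much experience improved on its own scale. For a small study meant to inform larger trials, that estimate is the more useful product.

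**Working it through.** **Nothing to reproduce.** The plan gives no alpha, power, effect size or rating distribution, so the check asks what the stated tests would cost if experience is graded.

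**Inputs.** From the plan: sets of 16, total 32, and the named tests. Assumed: a five-level rating, a proportional-odds shift, 16 versus 16, two-sided 5%, no dropout.

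**Shift.** For each cut of the scale, P₁/(1−P₁) = OR × P₀/(1−P₀). With a flat control distribution and OR 3, the top-two share moves from 0.40 (odds 0.667) to odds 2.0, that is 0.667. The full intervention distribution is (0.077, 0.105, 0.152, 0.238, 0.429).

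**Simulated power (%), 16 versus 16, 4,000 trials per row.** The cut separates the top two levels from the rest.

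| Control distribution | OR | Wilcoxon | Unordered 2×5 chi-squared | Fisher on cut | Uncorrected chi-squared on cut |
|---|---|---|---|---|---|
| Symmetric (.1,.2,.4,.2,.1) | 3 | 39.0 | 18.5 | 20.3 | 33.4 |
| Flat (.2 each) | 3 | 38.8 | 20.6 | 21.3 | 33.8 |
| Top-heavy (.05,.1,.2,.3,.35) | 3 | 36.6 | 17.9 | 13.7 | 27.3 |
| Symmetric | 4 | 56.2 | 29.9 | 34.0 | 49.6 |
| Flat | 4 | 54.5 | 32.4 | 32.2 | 46.5 |
| Top-heavy | 4 | 50.7 | 27.0 | 21.2 | 36.8 |

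The simulation standard error is at most √(0.25/4000) = 0.8 points. Separate simulations on the same assumptions gave these ranges, in the column order above:
- OR 3: 37–39, 17–21, 14–22 and 27–36.
- OR 4: 51–55, 27–32, 21–35 and 35–49.

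**Loss against Wilcoxon, row by row.**
- Unordered chi-squared: from 38.8 − 20.6 = 18.2 points to 56.2 − 29.9 = 26.3. A four-level scale (.15,.3,.35,.2) at OR 3 gives 36.8 − 22.4 = 14.4.
- Fisher on a cut: from 38.8 − 21.3 = 17.5 to 50.7 − 21.2 = 29.5.
- Uncorrected chi-squared on a cut: from 38.8 − 33.8 = 5.0 to 50.7 − 36.8 = 13.9. Across other cuts and up to OR 6 the range is about 1 to 21.

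**Part of the Fisher loss is conservatism.** With no true difference, Fisher rejected in 1.4–2.4% of these five-level trials, against 4.5–5.6% for Wilcoxon and 5.3–6.0% for uncorrected chi-squared on the cut.

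**Patients per arm for 80% power at OR 3, flat distribution.**
- Full scale (Whitehead): n = 6(z₀.₉₇₅ + z₀.₈₀)² / [(ln OR)²(1 − Σp̄ₖ³)]. The averaged proportions are (0.138, 0.152, 0.176, 0.219, 0.314), with Σp̄ₖ³ = 0.053. So n = 6 × 7.849 / (1.207 × 0.947) = 41.2, rounded up to 42.
- Top-two cut: n = [1.960√(2 × 0.533 × 0.467) + 0.842√(0.240 + 0.222)]² / 0.267² = 3.822 / 0.0711 = 53.7, rounded up to 54.

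The top-heavy case needs 46 against 75, or 54 with the best-placed cut. The cut therefore costs 54/42 = 1.29 to 75/46 = 1.63 times as many patients with a top-two split, and less if its position happens to be favourable.

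**Dependence on group size.** At 32 versus 32 and OR 3, the same five-level distributions give Wilcoxon 63–67%, unordered chi-squared 37–45%, Fisher on the cut 34–51% and uncorrected chi-squared on the cut 45–61%.

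**The case against.** The strongest reply is that the premise is inferred. No section says that experience is a rating, or that it comes from the questionnaires. It could be one yes/no item, for which the named tests are suitable, or partly qualitative, since recordings are reviewed for themes. The descriptive sentence on means and standard deviations also covers demographics, so age alone could account for it. This stands, and it is why the point is conditional and why the fix starts with defining the measure.

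A reader might also infer that the adjusted model must be binary logistic regression and so loses the order too. The text says only logistic regression, which can include the proportional-odds form. That reading is not supported, although the unadjusted test is unaffected by it.

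A reader might further conclude that the plan always forfeits much of the power. That follows only if unordered chi-squared or Fisher is used. The plan equally allows chi-squared on a cut and says nothing of a continuity correction; uncorrected, the usual loss is about 5–15 points. That milder case is not assured. In the top-heavy example at OR 3, the expected count outside the top two levels is 16 × (0.35 + 0.15)/2 = 4 per group, where many analysts would switch to Fisher.

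Finally, experience is an additional hypothesis, not a primary outcome. The Wilcoxon test itself reaches only about 37–39% at OR 3 and 51–55% at OR 4. Both facts stand and limit the priority. The correction is still worthwhile because experience is a stated hypothesis and the change costs almost nothing.

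**Conclusion.** The point holds in conditional form. The plan hypothesises better experience, leaves the measure undefined, and prescribes for every outcome an unadjusted test that does not suit a graded or continuous score. On the assumptions above, the power loss at odds ratios 3 to 4 is roughly 15–30 points for unordered chi-squared or for Fisher on a cut. It is usually about 5–15 points for uncorrected chi-squared on a cut, and nil for a single yes/no item.

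These figures should not be read as applying to whatever comparison group is eventually used. Design & Procedures discharges both sets of 16 on the new or revised model, which accounts for all 32 participants, and no usual-care group is described. Power depends on that group's size. The missing comparator is a separate and larger problem that this change does not solve. Nor does the change make the experience comparison well powered. Its gain is a test that matches the hypothesis and an effect estimate on the full scale.

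**What to change.** In Data Analysis & Statistical Considerations:

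1. State the patient-experience measure, how it is collected, its response levels and its scoring. If it is a single yes/no item, say so; the existing tests then suffice for it.
2. Limit chi-squared and Fisher's exact tests to binary or unordered outcomes, and binary logistic regression to binary ones.
3. Add text such as: *An ordinal or summed patient-experience score will be compared on its full scale by the Wilcoxon rank-sum test. It will be reported with the probability that a patient in one group scores higher than a patient in the other, and a 95% confidence interval. Any adjusted comparison will use proportional-odds regression, or linear regression for a summed score. Percentages above a cut-point will be descriptive only.*

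The cost is a few sentences, with no new data, patients or procedures. The one downside is that a rank-based effect is slightly less familiar than a percentage, and the percentage can still be shown alongside it.
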